9. CORRELATIVE/SPECIAL STUDIES

9.1 Laboratory Correlative Studies

Capecitabine pharmacokinetics: Plasma samples for the analysis of capecitabine and metabolites (5-FU, DFCR, and DFUR) will be obtained at baseline (prior to dosing) and 1, 2, 3, 4, 6, and 8 hours after administration on day 1 and day 9 of cycle 1 and at steady state on cycle 1 days 7 and 15. Plasma and tissue concentrations will be measured by HPLC as previously described.³⁸. For 5FU, the standard curve is linear from 0.019 to 20 μ g/ml, r2 = 0.999, with an intraday variability ranging from 4.49%-5.52% over the standard curve. Inter-day variability over 2 weeks ranges from 4.33-5.42% over the standard curve and the lower limit of quantitation (LLOQ) is 0.0195 μ g/ml. For capecitabine, the standard curve is linear from 0.019 to 20 μ g/ml, r2 = 0.999, with intraday variability ranging from 1.2-7.8% and inter-day variability from 7.6-13.9% over 3 months and a LLOQ of 0.019 μ g/ml. The standard curves for DFCR and DFUR are both linear from 0.625 to 40 μ g/ml, r2 = 0.999, with an intraday variability over 4 weeks ranging from 3.45%-6.36% and 4.24-6.45% and LLOQ of 0.312 μ g/ml and 0.0195 μ g/ml, respectively.

Pharmacokinetic variables will be determined by noncompartmental methods with WinNonlin Pro version 5.2 (Pharsight Corporation, Cary, N.C.). Area under the plasma concentration–time curve is estimated using the trapezoidal rule from time 0 to peak concentration and the log-trapezoidal rule from the peak concentration to the last measurable plasma concentration (AUClast). AUC($0-\infty$) is then calculated from the time of dosing and extrapolated to infinity.

9.2 **PK Sample Collection**

Blood samples are collected in 6-mL EDTA (purple top) tubes at the timepoints described in Table 5, below on day 1, 7, 9 and 15 of cycle 1. Samples are then centrifuged at 3500RPM at 4°C to obtain plasma, aliquotted into cryovials and stored at -70C until analysis.

Time	Time
C1D1	C1D9
0 (prior to first capecitabine dose)	0 (prior to AM capecitabine dose)
1 hr post capecitabine dose	1 hr post capecitabine
2 hr post	2 hr post
3 hr post	3 hr post
4 hr post	4 hr post
6 hr post	6 hr post
8 hr post	8 hr post
C1D7	C1D15
0 (prior to AM dose of capecitabine)	0 (prior to AM capecitabine dose)

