13. STATISTICAL CONSIDERATIONS

13.1 Study Design/Endpoints

The primary endpoints are the PK parameters (AUC and Cmax) of capecitabine when dosed using actual versus ideal body weight. Secondary endpoints are response and progression-free survival.

A single arm study design will be used to characterize the effect on pharmacokinetic parameters of capecitabine, when dosed using actual versus ideal body weight. Ideal body with based dosing of capecitabine when be used for cycle 1 from day 1 to day 7 followed by an actual body weight based dosing from Day 9 to Day 15. There will be a wash-out period on Day 8.

PK parameters will be summarized in terms of number of observations, means, standard deviations, medians, and ranges, stratified by assessment time point. The noncompartmental method will be used to estimate PK parameters. AUC will be estimated using the Lagrange approximation method. A paired t-test will be used to compare the PK parameters between the full weight and limited weight based dosing. If the PK parameters are not normally distributed, then an appropriate transformation will be identified before conducting the comparison. The comparison of AUC and Cmax between full weight and limited based dosing will be also performed using a population pharmacokinetics analysis, based on a nonlinear mixed effects modeling approach.

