13.2 Sample Size/Accrual Rate

The primary objective is to characterize the effect on pharmacokinetic parameters when capecitabine is dosed on actual versus ideal body weight results in obese patients with advanced solid tumors. A mean difference in the AUC and Cmax of at least 30% between the ideal body weight dosing versus the actual body with based dosing will be considered as a minimal important difference. Based on the results of several previous PK studies involving capecitabine, it is anticipated that the overall standard deviation for the difference between the two dosing strategies is at most 25% of the mean difference. The following table shows the required sample sizes to detect various mean differences in PK parameters between the two dosing strategies at the two-sided 0.025 (=0.05/2 - a Bonferroni adjustment for comparing both AUC and Cmax) significance level with 80%

power, assuming a standard deviation ranging from 20-30%.

with 0070	power ai me inc	biaca 0.025 sig	infleance level				
	Mean difference in PK parameters between the ideal versus actual weight based dosing strategy						
Standard	20%	25%	30%	35%	40%		
Deviation							
20%	13	9	7	6	6		
25%	18	13	10	8	7		
30%	24	17	13	10	9		

Table 13.1: *Required sample sizes to detect various mean differences in PK parameters with 80% power at the two-sided 0.025 significance level*

A sample size of n=10 patients is proposed for this study. With a sample size of 10 patients, a clinically important difference of 30% between the ideal and actual body weight based dosing will be detected with 82% power at the one-sided 0.025 (=0.05/2 - a Bonferroni adjustment for evaluating both AUC and Cmax) significance level, assuming an overall standard deviation of 25%. A mean difference of only 25% will be detected with 68% power. Patients will be evaluable for the primary endpoint if he or she completes cycle 1, capecitabine therapy without dose reduction or skipped doses. Any patient who does not meet these criteria will be replaced.

The anticipated accrual is 1-2 patients per month. Therefore, the study is expected to be completed within 6-12 months after first accrual.

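### The scale of the primary AUC and Cmax comparison is left to be chosen after the data are seen, and the 30% target, the SD wording and the AUC rule are not pinned down; n=10 itself reproduces

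*Combined protocol and SAP*

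**What the plan says.** **Test and scale (Section 13.1).** AUC and Cmax are both primary. The plan states: "A paired t-test will be used to compare the PK parameters between the full weight and limited weight based dosing". It continues: "If the PK parameters are not normally distributed, then an appropriate transformation will be identified before conducting the comparison". It does not say which normality check is used, whether the check is applied to the differences or to each day's values, or which transformation follows. No ratio, percentage change or confidence interval is named for the primary comparison. A population pharmacokinetic comparison of the same two endpoints is added.

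**Planning (Section 13.2).** The smallest difference of interest is given as "A mean difference in the AUC and Cmax of at least 30" per cent, with no statement of what it is a percentage of. The text before Table 13.1 says that the "standard deviation for the difference between the two dosing strategies is at most 25% of the mean difference". The power statement after the table works "assuming an overall standard deviation of 25" per cent.

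**AUC rule.** Section 9.1 uses the linear trapezoidal rule up to the peak and then "the log-trapezoidal rule from the peak concentration to the last measurable plasma concentration", which gives AUClast. AUC(0-infinity) "is then calculated from the time of dosing and extrapolated to infinity". Section 13.1 says instead: "AUC will be estimated using the Lagrange approximation method", with no degree given. Neither section takes precedence, and neither says whether AUClast or AUC(0-infinity) is the primary endpoint.

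**The concern.** The stated objective is to characterize an effect, so the reported estimate is the main product of this trial. Two analysts could follow the plan faithfully and still report different things: a difference in arithmetic means or an effect on some transformed scale, from AUCs computed by different rules over different extents. The choice of scale depends on the same 10 pairs of values that are then tested. A normality check on so few values has little ability to detect skewness, so it is a weak guide to the scale.

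The planning figures do not settle the matter. Without a reference, a 30% difference can mean two different ratios. The SD sentence, read literally, describes a much smaller variability than the table assumes.

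**Working it through.** **1. The plan's own figures.** Inputs from Section 13.2: difference 30, SD 25, n=10, two-sided level 0.05/2 = 0.025 (the level in the table title). For a paired t-test, power is P(|T| > t(1−0.0125; n−1)), where T is noncentral t with n−1 degrees of freedom and noncentrality (difference/SD)·√n.

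- n=10: noncentrality 1.2 × 3.162 = 3.79, critical value 2.685, power 84.2%.
- n=9: noncentrality 3.60, power 78.1%.

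So n=10 is the smallest size that reaches 80%, and all 15 cells of Table 13.1 reproduce this way. A 25% difference gives 68.2%, against the stated 68%. The stated 82% at a 30% difference is close to 84.2% but does not match exactly. The power sentence calls the same 0.025 level one-sided; that would give 92.0% and 80.3%, so the figures rest on the two-sided level.

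**2. The SD wording.** Read literally, 25% of a 30-point difference is 7.5 points, an effect size of 30/7.5 = 4. Power would then be 98% at n=4. The table holds only with an SD of 25 points.

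**3. The reference for the 30%.** If ideal-weight exposure is the reference, the ratio is 1.30 (log 0.262). If actual-weight exposure is the reference, it is 1/0.7 = 1.43 (log 0.357). The same formula on log-ratios at n=10, with assumed SDs of the log-ratio, gives:

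| Ratio | log-SD 0.20 | log-SD 0.25 | log-SD 0.30 |
|---|---|---|---|
| 1.30 | 90% | 73% | 55% |
| 1/0.7 | 99% | about 94% | 84% |

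At ratio 1.30 and log-SD 0.25, n=11 gives 78.5% and n=12 gives 83.3%.

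**4. Cost of the conditional rule.** The plan names no check, so one has to be assumed: Shapiro-Wilk at 0.05 on the differences, with logs used if it rejects. The data are log-normal, with ratio 1.30 and log-ratio SD 0.219. That SD is chosen so that 0.262/0.219 = 1.2 matches the plan, which builds in 84% power for an always-log test. The between-patient CV r is assumed, because the documents give none for capecitabine.

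- CV 30%: the conditional rule has about 80 to 81% power against 84% for always-log. The two verdicts differ in about 6% of trials, and the test stays on the raw scale in about 89%.
- CV 50% and 85%: the conditional rule has about 78% and 75%.
- True ratio 1.00: rejection rates of about 0.020 to 0.025, so there is no inflation.

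The larger CVs are illustrative only. In this model the variance of the raw difference, as a fraction of the squared ideal-weight mean, is (1+CV²)·[(1+1.30²)·exp(0.219²/2) − 2×1.30] − 0.30², and the bracket equals 0.1553.

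- CV 30%: √(1.09×0.1553 − 0.09) = 28%.
- CV 50%: √(1.25×0.1553 − 0.09) = 32%.
- CV 85%: √(1.7225×0.1553 − 0.09) = 42%.

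Table 13.1 covers 20 to 30%, so only the first case lies inside the planned range.

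**5. The two AUC rules.** On illustrative one-compartment curves at the protocol's sampling times (half-life 0.75 h), Lagrange minus the Section 9.1 rule is +2% to +6% per curve if first-degree, and −4% to +18% if cubic. The discrepancy cancels in the Day 9/Day 1 ratio when a patient's absorption profile repeats. If profiles vary freely between days, the 10-patient ratio shifts by up to 0.8% (first-degree) or 6% (cubic, an upper bound). The part extrapolated beyond 8 h is 0.1 to 6% of AUC(0-infinity).

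**The case against.** The strongest reply is that the plan is coherent as it stands. Section 13.2 speaks of a mean difference and the SD of that difference, which is what a raw-scale paired t-test uses. A t-test does not depend on units: 30% and 25% of one reference mean give effect size 1.2 in concentration units too. The descriptive summaries in Section 13.1 include means by time point, so a percentage difference can be read off afterwards. All of this stands. A reader might infer that planning in percentages commits the trial to a log or ratio scale, or that a raw difference can never be set against the 30% target. The documents support neither inference.

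A reader might also infer a serious loss of power. That does not stand either. The larger losses need CVs that push the raw SD above the planned range, and the only documented figure above 85% (Section 2.3) is for 5-FU, not capecitabine. With the raw SD held at the planned 25%, the raw test has 89% power at CV 30% and 94% at CV 50%, above the planned 84%. The log test is still better in that setting (93% and 99%).

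It is fair to add that this is a 10-patient pilot, that the SD sentence looks like a slip, that the population analysis already reads as additional, and that the AUC conflict has little effect on a within-patient ratio if profiles repeat. The fixed meal timing in Section 5.1 gives some reason to expect that. These points limit the size of the problem. They do not supply the missing transformation, check, reference or AUC rule, and the plan itself sets a Bonferroni-adjusted test and a target difference.

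**Conclusion.** The primary analysis is under-specified and should be settled before the data are analysed. The scale depends on an unnamed check and an unnamed transformation, the 30% has no reference, the SD sentence contradicts Table 13.1, and Sections 9.1 and 13.1 conflict on a primary endpoint without naming its extent.

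The consequence is mainly for which effect is reported. The sample size stands and type I error is not inflated. The power cost of about 3 to 4 points rests on an assumed CV of 30%, a log-normal model with log-ratio SD 0.219, and Shapiro-Wilk applied to the differences. The AUC figures rest on illustrative curves, and the cubic ones also on a degree that the plan does not state.

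**What to change.** - **Section 13.1, test:** replace the conditional-transformation sentence with a paired t-test on log(AUC) and log(Cmax). Report the actual/ideal (Day 9/Day 1) geometric mean ratio with a 97.5% confidence interval, which matches the 0.025 level. Keep the untransformed comparison as a labelled sensitivity analysis and call the population analysis supportive.
- **Sections 9.1 and 13.1, AUC:** use the Section 9.1 rule in both, since it is already fully described, and name AUClast or AUC(0-infinity) as primary.
- **Section 13.2:** correct the SD wording to 25 percentage points, state whether the 30% means a ratio of 1.30 or 1/0.7, give an SD on the log scale, and restate the power for n=10.

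No new data, visits or software are needed, but the team has to make two real choices: the reference for the 30% and the log-scale SD. The downside is that restated power may fall below 80%. At ratio 1.30 and log-SD 0.25 it is 73% with n=10, and reaching 80% would take 12 patients.

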1. OBJECTIVES

1.1. **Primary Objective**: To characterize the effect on pharmacokinetic parameters of capecitabine, when dosed using actual versus ideal body weight in obese patients with advanced solid tumors.

1.2. Secondary Objectives:

1.2.1 To characterize the response rate and progression free survival with capecitabine therapy in obese subjects with advanced solid tumors

1.2.2 To determine capecitabine pharmacokinetics in obese patients compared with normal weight historical controls.

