Hepatobiliary Hyperbilirubinemia Net chemred	22	9	2		

NA = Not Applicable

Clinical Pharmacokinetics

Capecitabine is relatively non-cytotoxic in vitro. This drug is enzymatically converted to 5-fluorouracil (5-FU) in vivo. Capecitabine is readily absorbed from the gastrointestinal tract. In the liver, a 60 kDa carboxylesterase hydrolyzes much of the compound to 5'-deoxy-5-fluorocytidine (5'-DFCR). Cytidine deaminase, an enzyme found in most tissues, including tumors, subsequently converts 5'-DFCR to 5'-deoxy-5-fluorouridine (5'-DFUR). The enzyme, thymidine phosphorylase (dThdPase), then hydrolyzes 5'-DFUR to the active drug 5-FU. Many tissues throughout the body express thymidine phosphorylase. Some human carcinomas express this enzyme in higher concentrations than surrounding normal tissues.³⁶ Following oral administration of capecitabine 7 days before surgery in patients with colorectal cancer, the median ratio of 5-FU concentration in colorectal tumors to adjacent tissues was 2.9 (range from 0.9 to 8.0).

The pharmacokinetics of capecitabine and its metabolites have been evaluated in about 200 cancer patients over a dosage range of 500 to 3500 mg/m²/day.^{14,37} Over this range, the pharmacokinetics of capecitabine and its metabolite, 5'-DFCR were dose proportional and did not change over time. The increases in the AUCs of 5'-DFUR and 5-FU, however, were greater than proportional to the increase in dose and the AUC of 5-FU was 34% higher on day 14 than on day 1. The elimination half-life of both parent capecitabine and 5-FU was about 3/4 of an hour. The inter-patient variability in the C_{max} and AUC of 5-FU was greater than 85%.

Capecitabine reached peak blood levels in about 1.5 hours (T_{max}) with peak 5-FU levels occurring slightly later, at 2 hours. Food reduced both the rate and extent of absorption of capecitabine with mean C_{max} and AUC_{0-infinity} decreased by 60% and 35%, respectively. The C_{max} and AUC_{0-infinity} of 5-FU were also reduced by food by 43% and 21%, respectively. Food delayed T_{max} of both parent and 5-FU by 1.5 hours. Plasma protein binding of capecitabine and its metabolites is less than 60% and is not concentration-dependent. Capecitabine was primarily bound to human albumin (approximately 35%).

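### Section 13.2 contradicts itself on sidedness and SD: the power sentence names one-sided 0.025, but Table 13.1 and the printed 68% are two-sided, and the 82% fits neither

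*Combined protocol and SAP*

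**What the plan says.** The primary endpoints are AUC and Cmax of capecitabine under ideal-weight and then actual-weight dosing. Section 13.1 states: "A paired t-test will be used to compare the PK parameters between the full weight and limited weight based dosing". It gives no significance level and no sidedness.

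Section 13.2 supplies the level twice, each time with the same Bonferroni explanation (0.05/2 for two endpoints):

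- Before Table 13.1 and in its caption, the level is two-sided 0.025, with 80% power.
- After the table, for n=10, a "difference of 30% between the ideal and actual body weight based dosing will be detected with 82% power at the one-sided 0.025" level, assuming an SD of 25%. The next sentence adds: "A mean difference of only 25% will be detected with 68% power".

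The SD also appears in two forms. The justification says that the "standard deviation for the difference between the two dosing strategies is at most 25% of the mean difference". The table then runs over SDs of 20%, 25% and 30%, and the power sentence uses 25%.

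**The concern.** The significance level, its sidedness and the SD are the inputs that a reader needs to check n=10 and, later, to judge the primary result. Here the level attached to the stated power is not the one that the sample-size table uses.

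The difference is not cosmetic. One-sided 0.025 has the same critical value as an unadjusted two-sided 0.05 test, so the choice decides whether the Bonferroni step protects a two-sided or only a one-sided overall 0.05. With ten patients and an observed SD of 25 points, the smallest significant mean difference is 21.2 points at two-sided 0.025 and 17.9 points at one-sided 0.025. Because Section 13.1 is silent, an analyst could defend either after seeing the data.

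The SD wording matters in the same way. Taken literally, it describes a far less variable comparison than the one the table was built on.

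**Working it through.** **Inputs (Section 13.2).** n=10; differences of 30% and 25%; SD 25%; level 0.025; printed power 82% and 68%; the 15 sample sizes in Table 13.1.

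**Method.** Exact power of a paired t-test: df = n - 1, non-centrality = (difference/SD) × √n, with the critical value from the central t distribution. Percentages are treated as points on one scale, as the table does.

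**Step 1: reproduce Table 13.1.** Smallest n with at least 80% power, for differences of 20, 25, 30, 35 and 40%:

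| SD | Printed | Two-sided 0.025 | One-sided 0.025 |
|---|---|---|---|
| 20% | 13, 9, 7, 6, 6 | 13, 9, 7, 6, 6 | 10, 8, 6, 5, 5 |
| 25% | 18, 13, 10, 8, 7 | 18, 13, 10, 8, 7 | 15, 10, 8, 7, 6 |
| 30% | 24, 17, 13, 10, 9 | 24, 17, 13, 10, 9 | 20, 14, 10, 8, 7 |

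Two-sided matches 15 of 15 cells; one-sided matches none.

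**Step 2: power at n=10, SD 25%.** Non-centrality is (30/25) × √10 = 3.795 for 30%, and (25/25) × √10 = 3.162 for 25%. Critical values on 9 df are 2.685 (two-sided 0.025) and 2.262 (one-sided 0.025).

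| Difference | Printed | Two-sided 0.025 | One-sided 0.025 |
|---|---|---|---|
| 30% | 82% | 84.2% | 92.0% |
| 25% | 68% | 68.2% | 80.3% |

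The 68% is a two-sided figure. The 82% is about 2 points below the two-sided value and 10 below the one-sided value. A normal approximation does not rescue it: for a 30% difference that gives 94.0% two-sided and 96.7% one-sided.

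**Step 3: does n=10 survive?** At two-sided 0.025, n=9 gives 78.1% and n=10 gives 84.2%, so 10 is the smallest adequate size. At one-sided 0.025, n=7 gives 75.4% and n=8 gives 82.8%, so 10 is more than enough.

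**Step 4: the SD wording.** 25% of a 30% difference is 0.25 × 30 = 7.5 points. At two-sided 0.025 that gives 97.9% power with n=4 and above 99.9% with n=10. Neither the table nor the power sentence used that reading.

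**Step 5: smallest significant mean difference at n=10, observed SD 25.** 2.685 × 25/√10 = 21.2 points; 2.262 × 25/√10 = 17.9 points.

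**The case against.** The strongest reply is that this is a slip of wording in a pilot study. The table is internally sound, n=10 is right for it, and the SD actually used is plain from the table. That stands, and it limits the size of the point. It is also fair that the hypothesis in Section 2.4 is directional, so a one-sided test may have been intended. The figures favour two-sided, but the documents do not settle it, which is why the fix below offers both routes.

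A reader might infer two stronger things.

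The first is that the trial is underpowered. The documents do not support this: under either sidedness, n=10 gives at least 80% power for the 30% difference at SD 25%.

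The second is that the primary comparison is unsound. Both periods use the same dose per m², so each patient's dose ratio is fixed by √(actual/ideal weight) before rounding to 150 mg, and no dose-normalised comparison is planned. That reading goes too far, for three reasons.

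- The objective is "To characterize the effect on pharmacokinetic parameters of capecitabine, when dosed using actual versus ideal body weight in obese patients". That is total exposure under two dosing rules, and the paired test answers it.
- A patient's weight is essentially the same on Day 1 and Day 9. Exposure per mg within a patient therefore tests dose proportionality (plus any period effect), not an effect of obesity. Section 2.3 already reports that the parent drug's kinetics "were dose proportional and did not change over time".
- Ten patients give little precision. If the ratio of exposure per mg has a CV of 25% (an assumption), the log SD is √ln(1 + 0.25²) = 0.246 and the 95% interval factor is exp(2.262 × 0.246/√10) = 1.193. A true ratio of 1 would carry an interval of about 0.84 to 1.19 (0.87 to 1.15 at 20%; 0.81 to 1.23 at 30%).

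What remains is a presentational aid. The planned population PK analysis is described only as a further comparison of AUC and Cmax, so it is not certain to show how much of the rise simply follows the dose.

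**Conclusion.** Section 13.2 is wrong as written on two counts. The level named in the power sentence does not produce the printed power: one-sided 0.025 gives 92% and 80%, against 82% and 68% printed. The verbal SD assumption (7.5 points for a 30% difference) contradicts the 25% used. The table and the 68% are consistent with two-sided 0.025; the 82% should read 84% at that level, and its source cannot be recovered from the documents.

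These results rest on the paired t-test named in Section 13.1 and on reading the difference and SD in the same percentage points; the exact match of all 15 cells supports both. The sample size, the 30% minimal important difference and the primary comparison are unaffected.

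**What to change.** In Section 13.2, choose one level and use it throughout:

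- **Two-sided 0.025 (fits the existing table):** change the power sentence to two-sided, with 84% for a 30% difference and 68% for 25%. Table 13.1 and n=10 stay as they are.
- **One-sided 0.025, if truly intended:** restate power as 92% and 80%, change the text before the table and the caption, and replace the table with the one-sided values in the working above. n=10 can stay.

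State the chosen sidedness and level in Section 13.1 as well, next to the paired t-test. Reword the SD assumption to an SD of 25 percentage points for the paired difference, with 20-30 as the range examined.

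The cost is a few sentences, with no change to dosing, enrolment or sample size.

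Optional and secondary: report each patient's parent-capecitabine AUC and Cmax ratio (Day 9 to Day 1) beside the ratio of the rounded doses actually given, as description only. Do not read the same listing for 5-FU as a dose effect alone, since Section 2.3 reports that "the AUC of 5-FU was 34% higher on day 14 than on day 1". This uses data already collected.
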